4. Pregnancy test for females of child-bearing potential (FCBP). A female of childbearing potential is a sexually mature woman who: 1) has not undergone a hysterectomy or bilateral oophorectomy; or 2) has not been naturally postmenopausal (amenorrhea following cancer therapy does not rule out childbearing potential) for at least 24 consecutive months (i.e., has had menses at any time in the preceding 24 consecutive months). Pregnancy tests must occur within 10 – 14 days and again within 24 hours prior to prescribing lenalidomide (prescriptions must be filled within 7 days). FCBP with regular or no menstruation must have a pregnancy test weekly for the first 28 days and then every 28 days while on therapy (including breaks in therapy), at discontinuation of lenalidomide (whichever comes later) and at Day 28 post the last dose of lenalidomide (whichever comes later). FCBP with irregular menstruation must have a pregnancy test weekly for the first 28 days and then every 14 days while on therapy (including breaks in therapy), at discontinuation of lenalidomide (whichever comes later) and at Day 14 and Day 28 post the last dose of lenalidomide (whichever comes later) (see Appendix III: Risks of Fetal Exposure, Pregnancy Testing Guidelines and Acceptable Birth Control Methods).
5. Lenalidomide must be prescribed through and in compliance with Celgene's RevAssist® program. Prescriptions of lenalidomide must be filled within 7 days.
6. To occur within 6 weeks of treatment
7. Iliac crest bone marrow aspirate for cytological review, including cytogenetics, FISH studies, flow cytometry (when available), and core biopsy for immunohistochemistry.
8. To confirm complete remission, progression, or when clinically indicated
9. An additional safety assessment will be done 30 days (+/- 7 days) following the last dose of study drug.

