10.3 Day 1 (starting cycle 2) and End of Study

- Physical evaluation: A complete medical evaluation including medical history, adverse events, concomitant medications, physical exam, vital signs, KPS, height and weight.
- Complete Blood Count (CBC) with differential and platelet count.
- Complete metabolic profile (including sodium, potassium, chloride, CO₂, calcium, blood urea nitrogen (BUN), creatinine, glucose, albumin, total protein, alkaline phosphatase, total bilirubin, SGOT/AST, SGPT/ALT
- LDH
- Uric Acid
- TSH every 3 months beginning with cycle 4 (more often if clinically indicated)
- Serum protein electrophoresis, serum immunofixation, serum quantitative immunoglobulins
- Serum free light chains studies
- 24-hour urine collection for total protein, protein electrophoresis, and immunofixation.
- Prior cycle drug diary will be collected. New drug diary will be generated and reviewed with the patient.
- Serum pregnancy test, if applicable
- Bone marrow aspiration and biopsy to confirm a CR, or when clinically indicated.
- Skeletal survey, MRI, or whole body PET/CT scan when clinically indicated (i.e., to evaluate for disease response in non-secretory myeloma or to investigate for disease progression).
- All subjects will be followed for survival. Cause of death is to be recorded in the subject's medical record.
- Quality of Life assessment (Appendix IX)
- Second primary malignancies will be monitored as events of interest and should be included as part of the assessment of adverse events throughout the course of the study.

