14.0 STATISTICAL CONSIDERATIONS

14.1 Study Design/Primary Endpoint

The study is a randomized phase III design, and the primary endpoint in both treatment arms is median PFS. PFS will be defined as the time from randomization day until objective progression or death from any cause. The PFS distributions of the two treatment arms will be estimated by Kaplan-Meier survival analysis and the PFS distributions will be compared by an unstratified log-rank test. Ninety-five percent confidence intervals for the Kaplan-Meier PFS estimates will be calculated using

Greenwood's formulae. The primary comparison will be made using the intent-to-treat (ITT) patient population. Patients will be analyzed based on their randomization assignments, regardless of therapy initiation or compliance. A secondary analysis will be performed comparing "evaluable" patients as patients who met eligibility requirements, have initiated therapy, and were not removed from the study for non-compliance or patient withdrawal.

The median PFS for MM patients receiving Revlimid /dexamethasone chemotherapy (Rd) (Arm A) is expected to be approximately 25.5 months, as reported in the MM-010 study of continuous Rd vs Rd for 18 months (Facon T, Dimopoulos M, Dispenzieri A, et al: Initial phase 3 results of the FIRST trial in newly diagnosed multiple myeloma patients ineligible for stem cell transplant. 2013 ASH Annual Meeting. Abstract 2. Presented December 8, 2013.). Therefore, the target median PFS for patients receiving Revlimid/dexamethasone/Clarithromycin (BiRd) (Arm B) is hypothesized to be 44.6 months (target hazard ratio = 1.75).

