14.3 Analysis of Progression-Free Survival

Because the analysis of PFS can be difficult, especially in the presence of missing data and lost-to-follow-up, sensitivity analyses can be helpful in determining whether the PFS analysis is robust. As suggested by the alternative PFS definitions recommended in the FDA's Guidance for Industry, "Clinical Trial Endpoints for the Approval of Cancer Drugs and Biologics (May, 2007), the following three types of PFS analyses will be

conducted:

Table A. PFS #1 (includes documented progression only) (Primary PFS Analysis):

Situation	Date of Progression or Censoring	Outcome
No baseline tumor assessments	Randomization	Censored
Progression documented between scheduled visits	Earliest of: 
 • Date of hematological assessment showing progression; or • Date of radiological assessment showing progression; or • Date of urine assessment showing progression 	Progressed
No progression	Date of last hematological, radiological, or urine assessment	Censored
Treatment discontinuation for undocumented progression	Date of last hematological, radiological, or urine assessment	Censored
Treatment discontinuation for toxicity or other reason	Date of last hematological, radiological, or urine assessment	Censored
New anticancer treatment started	Date of last hematological, radiological, or urine assessment	Censored
Death before first PD assessment	Date of death	Progressed
Death between adequate assessment visits	Date of death	Progressed
Death or progression after more than one missed visit	If progression: 
 • Date of hematological assessment showing progression; or • Date of radiological assessment showing progression; or • Date of urine assessment showing progression OR, if not progression: Date of last hematological, radiological, or urine assessment	Censored

Table A represents the primary PFS analysis that only includes well-documented and verifiable progression events. Other data are censored. In Table A, the progression dates are 1) based only on radiological assessments verified by an IRC (clinical progression will not be considered a progression endpoint), 2) assigned to the first time when disease progression is noted, and 3) the date of death when the patient is closely followed. However, deaths occurring after two or missed visits will be censored at the last visit.

Table B. PFS #2 (uniform progression and assessment dates) (PFS Sensitivity Analysis #1):

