
  ≥50% reduction in the level of the serum monoclonal paraprotein.  Reduction in 24h urinary light chain excretion either by ≥90% or to <200mg.  For patients with light chain only disease, then a 50% reduction in the difference between the involved and unininvolved free light chain level may be substituted for the M-protein measurement.  For patients with non-secretory myeloma only, ≥50% reduction in plasma cells in a bone marrow aspirate and on trephine bone biopsy, if biopsy is performed.  ≥50% reduction in the size of soft tissue plasmacytomas (by radiography or clinical examination).  No increase in size or number of lytic bone lesion (development of a compression fracture does not exclude response)
Stable Disease (SD) requires the following:

  Not meeting the criteria stringent complete response (sCR), complete response (CR), very good partial response (VGPR), or partial response (PR)
Plateau:

  Stable values (within 25% above or below value at the time response is addressed) 
Patients in which no significant change (<50% decrease or <25% increase from baseline) in the production rate of the monoclonal serum protein or Bence-Jones protein excretion and no new lytic lesions and/or plasmacytomas are detected.

Relapse from CR requires at least one of the following:

- Reappearance of serum or urinary paraprotein on immunofixation or routine electrophoresis, confirmed by at least one further investigation and excluding oligoclonal immune reconstitution.
- ≥5% plasma in a bone marrow aspirate or trephine bone biopsy.
- Development of new lytic lesions of soft tissue plasmacytomas or definite increase in the size of residual bone lesions (development of a compression fracture does not exclude continued response and may not indicate progression).
- Development of hypercalcemia (corrected serum calcium >11.5mg/dl or 2.8 mmol/l) not attributable to any other cause.

Progressive disease (PD) for patients not in CR requires one or more of the following:

- >25 increase in the level of the serum monoclonal paraprotein, which must also be an absolute increase of at least 5g/L and confirmed by at least one repeated investigation.

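### Section 14.3 gives two incompatible rules for dating progression in the primary PFS analysis, and the progression criteria in Appendix I are incomplete for endpoint use

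*Combined protocol and SAP*

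**What the plan says.** Section 14.1 defines the endpoint: "PFS will be defined as the time from randomization day until objective progression or death from any cause". It does not say which criteria make progression objective. Section 14.3 then gives Table A as the primary PFS analysis. Its progression row takes the earliest of three dates, the first being "Date of hematological assessment showing progression; or", followed by the radiological and the urine date. The paragraph under the table, describing the same table, says progression dates are "based only on radiological assessments verified by an IRC (clinical progression will not be considered a progression endpoint".

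Imaging after screening is not on a fixed schedule. Section 1.3, footnote 8, gives its purpose as "To confirm complete remission, progression, or when clinically indicated", and section 10.3 lists "Skeletal survey, MRI, or whole body PET/CT scan when clinically indicated". Serum and urine M-protein and serum free light chains are taken on Day 1 of every cycle (sections 1.3 and 10.3).

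Appendix I has one list for relapse from CR and a second that opens "Progressive disease (PD) for patients not in CR requires one or more of the following". The serum criterion in the second list reads ">25 increase in the level of the serum monoclonal paraprotein, which must also be an absolute increase of at least 5g/L". The urine criterion has the same form with 200 mg/24h. The bone marrow criterion does carry the % sign. Section 10.11 uses Appendix I to define the progression that removes a subject from study.

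**The concern.** PFS is the only confirmatory endpoint, so the progression rule decides which patients have events and when. In myeloma followed by monthly serum and urine tests, a radiology-only rule is a different endpoint from the one in Table A. Progressions seen only in the laboratory would be censored, and the event count on which section 14.2 rests would not accrue as planned.

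Four further gaps bear on how events or responses are classified:

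- **Reference value.** The serum and urine criteria do not say from which value the increase is measured, so two assessors can date one patient's progression very differently in an open-label trial.
- **Relapse from CR.** Sections 14.1 and 14.3 do not expressly say that it is a PFS event.
- **Serum free light chain.** It can qualify a patient under section 5.1 and support PR in Appendix I, but a rise in it is not a progression criterion.
- **VGPR.** It is printed as a reduction of ≤90%, which a patient with no fall at all would satisfy if urine M-protein is below 100 mg. Section 14.4 labels the objective response rate CR+PR, while section 3.8 counts PR or greater. This touches response reporting only.

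**Working it through.** **Inputs from section 14.2.** Medians 25.5 (Rd) and 44.6 (BiRd) months, hazard ratio 1.75 (Rd over BiRd), two-sided 0.05, 153 per arm, 133 events, accrual 36 months, analysis at month 48, no dropout.

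**The plan's figure.** Schoenfeld events for 90% power: 4 × (1.960 + 1.282)² / (ln 1.75)² = 134.2, against 133 stated. Power with E events is Φ(½√E × ln 1.75 − 1.960); for E = 133 it is 0.897. The design reproduces.

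**Timing.** With hazard λ = ln 2 / median, the probability of an event by month T is 1 − (e^(−λ(T−36)) − e^(−λT)) / (36λ). At month 48 this is 0.540 (Rd) and 0.364 (BiRd), so 153 × (0.540 + 0.364) = 138.3 events are expected. The 133rd is expected at about month 46.5.

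**Radiology-only rule, same calendar date.** Two inputs are assumptions that the documents do not give: d, deaths without progression as a share of PFS events (20-40%), and r, the share of progressions that show on imaging (25-75%). The countable share is s = d + (1 − d) × r, and events are 133 × s.

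| d | r | s | events | power |
|---|---|---|---|---|
| 20% | 25% | 0.40 | 53 | 0.532 |
| 20% | 50% | 0.60 | 80 | 0.705 |
| 20% | 75% | 0.80 | 106 | 0.823 |
| 40% | 25% | 0.55 | 73 | 0.668 |
| 40% | 50% | 0.70 | 93 | 0.770 |
| 40% | 75% | 0.85 | 113 | 0.845 |

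**Radiology-only rule, waiting for 133 events.** Solve s × 153 × (p_Rd + p_BiRd) = 133 for T:

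- s = 1: month 46.5
- s = 0.80: month 57.0
- s = 0.60: month 82.6
- s below 133/306 = 0.435: not reached in 306 patients under this model

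The model treats a patient with laboratory-only progression as never having a later countable imaging event or death, so it overstates the loss and the delay.

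**Reference value.** Take an assumed fall in serum M-protein from 40 to 16 g/L, and read the criterion as more than 25% and at least 5 g/L.

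- From the lowest value: 16 × 1.25 = 20 and 16 + 5 = 21, so progression is met at 21 g/L.
- From baseline: 40 × 1.25 = 50 and 40 + 5 = 45, so progression is met only above 50 g/L.

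For urine falling from 1,000 to 150 mg/24h, the limits are 150 + 200 = 350 mg/24h from the lowest value and above 1,000 × 1.25 = 1,250 mg/24h from baseline. The Plateau entry in Appendix I does not settle the matter, because it refers both to the value when response is assessed and to baseline.

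**Missing % sign.** If 25 meant g/L, the added requirement of 5 g/L would be redundant. With the % sign present in the marrow criterion, this is evidently a printing slip.

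**The case against.** **Table A is plainly the intent.** Most of its progression and censoring rows name blood and urine assessments, and section 14.3 later says the primary analysis uses the progression times actually reported. That is persuasive about intent. But the conflicting sentence claims to describe Table A itself, so the text still needs reconciling.

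**The power loss is a worst case.** A reader might infer from the table above that the trial would have as little as 53% power. The documents do not support that as a prediction. Section 14.2 requires 133 events, so an analysis that waits for them loses mainly time, and the shares used are assumptions.

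**Relapse from CR is progression on a natural reading.** In Appendix I it is the counterpart of the list for patients not in CR, and its bone lesion entry itself speaks of what may not indicate progression. This stands. A reader might infer that CR patients could fail only by death, and so that the higher CR rate expected with BiRd (45.8% vs 13.9% in section 3.8, retrospective) would tilt PFS in its favour. That needs relapses in CR patients to go uncounted, which Appendix I does not suggest. Deaths count in any case under section 14.1. Table C also already counts an investigator's claim of progression and censors at new treatment only where there is no such claim, although it does not settle the primary rule.

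**Patients measurable only by free light chain can still progress.** True: the urine, marrow, bone lesion, plasmacytoma and hypercalcemia criteria remain. What is absent is progression by the qualifying marker. No size can be put on this from the documents.

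**IMWG criteria are understood.** Sections 2.2 and 10.11 name them but point to Appendix I as the text. Outside criteria would not cure the conflict inside section 14.3.

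**Conclusion.** The concern holds. Section 14.3 contradicts itself on how the primary endpoint is dated, and this is the main defect. If the radiology-only sentence were applied, the illustration gives 53-113 events in place of 133 and power of about 53-85% in place of 90% at a fixed date. Waiting for 133 events would move the analysis from about month 46.5 to about month 57 (80% of events countable) or month 83 (60%). These figures rest on the assumed death and imaging shares, exponential PFS and no dropout. They measure one reading of the text and do not forecast the trial.

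The missing reference value is also real and can shift a patient's progression date substantially. The silence on relapse from CR is a gap in wording, with a natural reading available. The free light chain omission is real but unquantified. The VGPR and response-rate wording does not affect the primary test. No imbalance between arms is claimed for any of these points, and the sample size calculation is not in dispute.

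**What to change.** 1. In section 14.3, remove or rewrite the radiology-only/IRC sentence so that the primary analysis dates progression as Table A does.
2. In section 14, for the PFS endpoint only and before data are reviewed, write >25% with one stated reference value for the serum and urine criteria. State whether relapse from CR is an event, and whether and how serum free light chain progression counts. Analyse the alternative CR rule as a pre-specified sensitivity analysis, noting what Table C already covers. The reference value and the CR rule are the sponsor's choice.
3. Correct VGPR to ≥90% and label the objective response rate as PR or better.

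Because section 10.11 ties removal from study to Appendix I, the sponsor must reconcile Appendix I, section 10.11 and section 14. No clinical rule is proposed here.

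The cost is text edits and one extra sensitivity analysis. No new measurement is needed, since serum and urine M-protein and serum free light chains are already taken every cycle.

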Appendix II: Diagnostic and Staging Criteria for Multiple Myeloma³³

International Myeloma Working Group (IMWG) Guidelines for the diagnosis of Multiple Myeloma

Definition of multiple myeloma

Clonal bone marrow plasma cells $\geq 10\%$ or biopsy-proven bony or extramedullary plasmacytoma* and any one or more of the following myeloma defining events:

- Myeloma defining events:
 - Evidence of end organ damage that can be attributed to the underlying plasma cell proliferative disorder, specifically:
 - Hypercalcaemia: serum calcium >0.25 mmol/L (>1 mg/dL) higher than the upper limit of normal or >2.75 mmol/L (>11 mg/dL)
 - Renal insufficiency: creatinine clearance <40 mL per min † or serum creatinine >177 μ mol/L (>2 mg/dL)
 - Anaemia: haemoglobin value of >20 g/L below the lower limit of normal, or a haemoglobin value <100 g/L
 - Bone lesions: one or more osteolytic lesions on skeletal radiography, CT, or PET-CT ‡
 - Any one or more of the following biomarkers of malignancy:
 - Clonal bone marrow plasma cell percentage* $\geq 60\%$
 - Involved:uninvolved serum free light chain ratio§ ≥ 100
 - >1 focal lesions on MRI studies¶

Definition of smoldering multiple myeloma

Both criteria must be met:

- Serum monoclonal protein (IgG or IgA) ≥ 30 g/L or urinary monoclonal protein ≥ 500 mg per 24 h and/or clonal bone marrow plasma cells 10–60%
- Absence of myeloma defining events or amyloidosis

PET-CT=¹⁸F-fluorodeoxyglucose PET with CT. *Clonality should be established by showing κ/λ -light-chain restriction on flow cytometry, immunohistochemistry, or immunofluorescence. Bone marrow plasma cell percentage should preferably be estimated from a core biopsy specimen; in case of a disparity between the aspirate and core biopsy, the highest value should be used. † Measured or estimated by validated equations. ‡ If bone marrow has less than 10% clonal plasma cells, more than one bone lesion is required to distinguish from solitary plasmacytoma with minimal marrow involvement. §These values are based on the serum Freelite assay (The Binding Site Group, Birmingham, UK). The involved free light chain must be ≥ 100 mg/L. ¶Each focal lesion must be 5 mm or more in size.

Diagnosis	Diagnostic Criteria: All Three Required
Symptomatic multiple myeloma ^a	
 • Monoclonal plasma cells in the bone marrow $>/=10\%$ and/or presence of a biopsy-proven plasmacytoma • Monoclonal protein present in the serum and/or urine^b • Myeloma-related organ dysfunction ($>/=1$)^c 
 [C] Calcium elevation in the blood (serum calcium >10.5 mg/l or upper limit of normal) [R] Renal insufficiency (serum creatinine >2 mg per 100 ml) [A] Anemia (hemoglobin <10 g per 100 ml or 2 g $<$normal) [B] Lytic bone lesions or osteoporosis^d
Monoclonal gammopathy of undetermined significance (MGUS)	
 • Serum monoclonal protein low^e • Monoclonal bone marrow plasma cells $<10\%$ • No evidence of end-organ damage attributable to the clonal plasma cell disorder: 
 ◦ Normal serum calcium, hemoglobin level and serum creatinine ◦ No bone lesions on full skeletal X-ray survey and/or other imaging if performed ◦ No clinical or laboratory features of amyloidosis or light chain deposition disease
Smoldering or indolent myeloma ^f	
 • Monoclonal protein present in the serum 3 g per 100 ml or higher or • Monoclonal plasma cells 10% or greater present in the bone marrow and/or a tissue biopsy • No evidence of end-organ damage attributable to the clonal plasma cell disorder: 
 ◦ Normal serum calcium, haemoglobin level and serum creatinine ◦ No bone lesions on full skeletal X-ray survey and/or other imaging if performed

	
 ○ No clinical or laboratory features of amyloidosis or light chain deposition disease
Solitary plasmacytoma of bone	
 ● Biopsy-proven plasmacytoma of bone in a single site only. X-rays and magnetic resonance imaging and/or ● FDG PET imaging (if performed) must be negative outside the primary site. ● The primary lesion may be associated with a low serum and/or urine M-component ● The bone marrow contains no monoclonal plasma cells ● No other myeloma-related organ dysfunction

Adapted with permission from Kyle and Rajkumar, [Criteria for diagnosis, staging, risk stratification and response assessment of multiple myeloma](#). *Leukemia* 2009; 23: 3–9.

^aThese criteria identify Stage IB and Stages II and III A/B myeloma by Durie/Salmon stage. Stage IA becomes smoldering or indolent myeloma.

^bIf no monoclonal protein is detected (non-secretory disease), then $\geq 30\%$ monoclonal bone marrow plasma cells and/or a biopsy-proven plasmacytoma required.

^cA variety of other types of end-organ dysfunctions can occasionally occur and lead to a need for therapy. Such dysfunction is sufficient to support classification as myeloma if proven to be myeloma related.

^dIf a solitary (biopsy-proven) plasmacytoma or osteoporosis alone (without fractures) is the sole defining criteria, then $\geq 30\%$ plasma cells are required in the bone marrow.

^eLow is defined as serum M protein <3.0 g per 100 ml.

^fThese criteria identify Stage IA myeloma by Durie/Salmon stage.

Salmon-Durie Staging System

Stage	Criteria
I	All of the following present:
	Hemoglobin > 10 g/dL
	Serum IgG < 5 g/dL
	Serum IgA < 3 g/dL
	Normal serum calcium
	Urine monoclonal protein excretion < 4 g/day
	No lytic bone lesions
II	Fulfills neither stage I nor stage III criteria
III	One of more of the following present
	Hgb < 8.5 g/dL
	Serum IgG > 7 g/dL
	Serum IgA > 5 g/dL
	Serum calcium > 12 mg/dL (3 mmol/L)

	Urine monoclonal protein excretion $> 12\text{g/day}$
	Multiple lytic bone lesions
Subcategory	
A	Serum creatinine $< 2\text{mg/dL}$ ($177\text{ }\mu\text{mol/L}$)
B	Serum creatinine $\geq 2\text{mg/dL}$

International Staging System (ISS)

Stage	Criteria
I	$\beta 2\text{-microglobulin} < 3.5\text{ mg/dL}$
	Serum albumin $\geq 3.5\text{ g/dL}$
II	Neither stage I nor stage II
III	$\beta 2\text{-microglobulin} \geq 5.5\text{ mg/dL}$

APPENDIX III: Risks of Fetal Exposure, Pregnancy Testing Guidelines and Acceptable Birth Control Methods

Risks Associated with Pregnancy

The use of lenalidomide in pregnant females and nursing mothers has not been studied nor has the effect of the lenalidomide on human eggs and sperm. The risks to a fetus are not known. However, because lenalidomide is related to thalidomide, and thalidomide is known human teratogenic active substance that causes severe life-threatening birth defects. An embryofetal development study in animals indicates that lenalidomide produced malformations in the offspring of female monkeys who received the drug during pregnancy. The teratogenic effect of lenalidomide in humans cannot be ruled out. Therefore, a risk minimization plan to prevent pregnancy must be observed.

All study participants must be registered into the mandatory RevAssist® program, and be willing and able to comply with the requirements of RevAssist®.

Females of childbearing potential (FCBP)† must agree to use two reliable forms of contraception simultaneously or to practice complete abstinence from heterosexual intercourse during the following time periods related to this study: 1) for at least 28 days before starting study drug; 2) while participating in the study; and 3) for at least 28 days after discontinuation from the study. The two methods of reliable contraception must include one highly effective method (i.e. intrauterine device (IUD), hormonal [birth control pills, injections, or implants], tubal ligation, partner's vasectomy) and one additional effective (barrier) method (i.e. latex condom, diaphragm, cervical cap). FCBP must be referred to a qualified provider of contraceptive methods if needed.

Counseling

For a female of childbearing potential, lenalidomide is contraindicated unless all of the following are met (i.e., all females of childbearing potential must be counseled concerning the following risks and requirements prior to the start of lenalidomide study therapy):

- She understands the potential teratogenic risk to the unborn child
- She understands the need for effective contraception, without interruption, 4 weeks before starting study treatment, throughout the entire duration of study treatment, dose interruption and 28 days after the end of study treatment
- She should be capable of complying with effective contraceptive measures

† A female of childbearing potential is a sexually mature woman who: 1) has not undergone a hysterectomy or bilateral oophorectomy; or 2) has not been naturally postmenopausal for at least 24 consecutive months (i.e., has had menses at any time in the preceding 24 consecutive months).

- She is informed and understands the potential consequences of pregnancy and the need to notify her study doctor immediately if there is a risk of pregnancy
- She understands the need to commence the study treatment as soon as study drug is dispensed following a negative pregnancy test
- She understands the need and accepts to undergo pregnancy testing based on the frequency outlined in this protocol
- She acknowledges that she understands the hazards and necessary precautions associated with the use of lenalidomide

The investigator must ensure that for females of childbearing potential:

- Complies with the conditions for pregnancy risk minimization, including confirmation that she has an adequate level of understanding
- Acknowledge the aforementioned requirements

For a female NOT of childbearing potential, lenalidomide is contraindicated unless all of the following are met (i.e., all females NOT of childbearing potential must be counseled concerning the following risks and requirements prior to the start of lenalidomide study therapy):

- She acknowledges that she understands the hazards and necessary precautions associated with the use of lenalidomide

Traces of lenalidomide have been found in semen. Male patients taking lenalidomide must meet the following conditions (i.e., all males must be counseled concerning the following risks and requirements prior to the start of lenalidomide study therapy):

- Understand the potential teratogenic risk if engaged in sexual activity with a pregnant female or a female of childbearing potential
- Understand the need for the use of a condom even if he has had a vasectomy, if engaged in sexual activity with a pregnant female or a female of childbearing potential.

Contraception

Females of childbearing potential (FCBP) enrolled in this protocol must agree to use two reliable forms of contraception simultaneously or to practice complete abstinence from heterosexual contact during the following time periods related to this study: 1) for at least 28 days before starting study drug; 2) while participating in the study; 3) dose interruptions; and 4) for at least 28 days after study treatment discontinuation.

The two methods of reliable contraception must include one highly effective method and one additional effective (barrier) method. FCBP must be referred to a qualified provider of contraceptive methods if needed. The following are examples of highly effective and additional effective methods of contraception:

- Highly effective methods:
 - Intrauterine device (IUD)

- Hormonal (birth control pills, injections, implants)
- Tubal ligation
- Partner's vasectomy
- Additional effective methods:
 - Male condom
 - Diaphragm
 - Cervical Cap

Because of the increased risk of venous thromboembolism in patients with multiple myeloma taking lenalidomide and dexamethasone, combined oral contraceptive pills are not recommended. If a patient is currently using combined oral contraception the patient should switch to one of the effective method listed above. The risk of venous thromboembolism continues for 4 to 6 weeks after discontinuing combined oral contraception. The efficacy of contraceptive steroids may be reduced during co-treatment with dexamethasone

Implants and levonorgestrel-releasing intrauterine systems are associated with an increased risk of infection at the time of insertion and irregular vaginal bleeding. Prophylactic antibiotics should be considered particularly in patients with neutropenia.

Pregnancy testing

Medically supervised pregnancy tests with a minimum sensitivity of 25 mIU/mL must be performed for females of childbearing potential, including females of childbearing potential who commit to complete abstinence, as outlined below.

Before starting study drug:

Female Subjects:

- FCBP must have two negative pregnancy tests (sensitivity of at least 25 mIU/mL) prior to prescribing lenalidomide. The first pregnancy test must be performed within 10-14 days prior to prescribing lenalidomide and the second pregnancy test must be performed within 24 hours prior to prescribing lenalidomide (prescriptions must be filled within 7 days). The subject may not receive study drug until the Investigator has verified that the results of these pregnancy tests are negative.

Male Subjects:

- Must practice complete abstinence or agree to use a condom during sexual contact with a pregnant female or a female of childbearing potential while participating in the study, during dose interruptions and for at least 28 days following study drug discontinuation, even if he has undergone a successful vasectomy.

During study participation and for 28 days following discontinuation from the study:

All Subjects:

- If pregnancy or a positive pregnancy test does occur in a study subject or the partner of a male study subject during study participation, lenalidomide must be immediately discontinued.

Female Subjects:

- FCBP with regular or no menstrual cycles must agree to have pregnancy tests weekly for the first 28 days of study participation and then every 28 days while on study, at study discontinuation, and at day 28 following discontinuation from the study. If menstrual cycles are irregular, the pregnancy testing must occur weekly for the first 28 days and then every 14 days while on study, at study discontinuation, and at days 14 and 28 following discontinuation from the study.
- In addition to the required pregnancy testing, the Investigator must confirm with FCBP that she is continuing to use two reliable methods of birth control at each visit.
- If pregnancy or a positive pregnancy test does occur in a study patient, study drug must be immediately discontinued.
- Pregnancy testing and counseling about pregnancy precautions and the potential risks of fetal exposure must be conducted at a minimum of every 28 days and must be performed if a subject misses her period or if her pregnancy test or her menstrual bleeding is abnormal. Study drug treatment must be discontinued during this evaluation.
- Females must agree to abstain from breastfeeding during study participation and for at least 28 days after study drug discontinuation.

Male Subjects:

Must agree to use a latex condom during sexual contact with females of childbearing potential while participating in the study and for at least 28 days following discontinuation from the study even if he has undergone a successful vasectomy.

- Counseling about the requirement for complete abstinence or condom use during sexual contact with a pregnant female or a female of childbearing potential and the potential risks of fetal exposure to lenalidomide must be conducted at a minimum of every 28 days.
- If pregnancy or a positive pregnancy test does occur in the partner of a male study patient during study participation, the investigator must be notified immediately.

Additional precautions

- Patients should be instructed never to give this medicinal product to another person and to return any unused capsules to the study doctor at the end of treatment.

- Female patients should not donate blood during therapy and for at least 28 days following discontinuation of study drug.
- Male patients should not donate blood, semen or sperm during therapy or for at least 28 days following discontinuation of study drug.
- Only enough study drug for one cycle of therapy may be dispensed with each cycle of therapy.

